9.1.1. Footnotes for the Schedule of Events Table

1. Patients who fail screening may be screened 1 additional time and an ICF will need to be signed at the re-screen. Some procedures may not need to be repeated if they were previously completed within 28 days prior to cycle 1 day 1.
2. Cycle 1 is 7 weeks long, cycles 2 through 4 are 6 weeks long, and all subsequent cycles are 9 weeks long.
3. Due to ± 3 -day windows of visits, the last day of a cycle may coincide with the first day of the next cycle (eg, C1D50 may be the same visit as C2D1, etc).
4. Patients who discontinue study drug due to progression of disease should proceed to the EOT visit, safety follow-up, and survival follow-up.
5. Patients who discontinue study drug for reasons other than progression of disease (as detailed in Section 7.3 and Section 8.2.2) should proceed to the EOT visit, safety follow-up, and tumor assessments. If these patients experience progression during tumor assessments, they should proceed to survival follow-up.
6. Informed consent must be provided before the initiation of screening procedures and must be obtained within 45 days prior to cycle 1 day 1. All screening assessments must be performed within 28 days prior to cycle 1 day 1 (for tumor tissue sample, see Section 9.2.1.1). Assessments performed as part of standard of care that fall within the screening window, but before informed consent is obtained, may be used for screening and need not be repeated for enrollment eligibility.
7. Local electrocardiograms (ECG) should be performed before blood is drawn during visits requiring blood draws.
8. On days when cemiplimab and ISA101b are administered together, cemiplimab will be administered first, and ISA101b will be administered approximately 1 hour after the end of the cemiplimab infusion.
9. Patients must be observed for 4 hours after each ISA101b administration.
10. During the treatment period, imaging should be acquired in the window of the scheduled imaging day (scheduled imaging day ± 7 days). Brain imaging is optional as clinically indicated.
11. If the EOT visit falls within 30 days of the last cycle tumor assessment, the CT scan and/or MRI does not need to be repeated.
12. If cycle 1 day 1 is within 72 hours of screening, this assessment does not need to be repeated at cycle 1 day 1.
13. Complete physical examination includes head and neck, lungs, heart, abdomen, lymph nodes, extremities, and skin. A brief neurologic examination should also be performed.
14. Limited physical exam includes lungs, heart, abdomen, and skin.
15. Vital signs are collected within 10 minutes prior to infusion, and approximately 15 minutes (± 10 minutes) after the completion of the infusion. Vital signs will also be taken every hour

during the 4-hour observation after administration of ISA101b. Note: Blood pressure should be measured after the patient has been resting quietly for at least 5 minutes. Blood pressure may be obtained from a seated or recumbent position and should be done consistently throughout the study. When scheduled at the same time as other procedures, vital signs should be measured prior to clinical laboratory assessments, PK, or exploratory sample collection.

16. Hematology and chemistry samples may be obtained ≤ 72 hours prior to cemiplimab treatment.
17. Pre-dose serum or urine β -human chorionic gonadotropin (HCG) up to 72 hours prior to study drug administration. Serum/urine pregnancy tests are requirements for women of child bearing potential only.
18. Serum samples for cemiplimab concentration will be collected from all patients pre-dose (C_{trough}) on cycle 1 day 1 and every other cycle for the first 2 years of treatment. After 2 years, samples for cemiplimab concentration will be collected pre-dose every 6 months (24 weeks) during therapy and at EOT.
19. ADA serum samples for cemiplimab will be collected pre-dose of cemiplimab administration on day 1 of cycle 1, and pre-dose of cemiplimab on day 1 of cycles 3 and 5 for the first year of treatment, then pre-dose every 4 cycles for the subsequent years of treatment (eg, C9, C13 and so on) and at EOT. In the event of AESI, additional samples may be collected for ADA analysis at or near the event when possible.
20. Peripheral blood mononuclear cell (PBMC) collection is optional. PBMC samples will be collected pre-dose on day 1, 8, and 29 of cycle 1, pre-dose on day 1 of cycles 2 through 4, day 1 of cycles 5+, and at end of treatment.
21. Pharmacogenomics (optional sub-study): See Section [9.2.10](#).

9.1.2. End of Treatment Visit

All patients will attend an end of treatment visit 30 days after their last dose of study drug.

Patients who are withdrawn from the study before the primary endpoint visit (cycle 4 day 43) will be asked to return to the clinic once for an end of treatment visit consisting of the assessments described in [Table 2](#).

9.1.3. Unscheduled Visits

All attempts should be made to keep patients on the study schedule. Unscheduled visits may be necessary to repeat testing following abnormal laboratory results, for follow-up of AEs, or for any other reason, as warranted.

9.1.4. Follow-Up

After progression, patients will complete end of treatment visit, safety follow-up visit, and have survival follow-up approximately every 4 months ([Table 2](#)).

Patients who discontinue study drug for reasons other than progression will be followed approximately every 4 months by scans until disease progression or until patient commences another anticancer systemic therapy, whichever comes first.

After progression, survival follow-up should occur approximately every 4 months. This may be done by phone contact.

9.2. Study Procedures

9.2.1. Procedures Performed Only at the Screening Visit

The following procedures will be performed for the sole purpose of determining study eligibility or characterizing the baseline population:

- Inclusion/exclusion criteria
- Informed consent
- Medical history and demographics
- Tumor tissue sample for documentation of pathologic confirmation of cervical cancer and HPV16 diagnostic testing
- HBV, HCV, and HIV testing

Patients who fail screening may be screened 1 additional time. Some procedures may not need to be repeated if they were previously completed within 28 days prior to cycle 1 day 1, and an ICF will need to be re-signed if prior ICF signing is beyond 45 days of cycle 1 day 1.

9.2.1.1. HPV16 Diagnostic Test

For HPV16 determination, a formalin-fixed, paraffin-embedded tissue block or unstained slides of tumor samples must be provided after the ICF is signed. Tumor biopsies should be of sufficient size or quantity to ensure an adequate amount of tissue for analysis. Complete instructions on the collection, processing, handling and shipment of all samples will be provided in the laboratory manual. A validated assay at a central laboratory will be used for determination of HPV16 genotyping in patient samples and to determine eligibility based on HPV16 positivity. Samples should be sent to the central laboratory at any point during the period between ICF signing and cycle 1 day 1 (including prior to the screening period; effort should be made to ship the sample just after the ICF is signed to ensure the result is received on time to confirm eligibility). The use of HPV16 for decisions regarding treatment with ISA101/ISA101b is considered investigational.

9.2.2. Efficacy Procedures

9.2.2.1. Computed Tomography and/or Magnetic Resonance Imaging

Diagnostic quality contrast-enhanced CT and contrast-enhanced MRI are the preferred imaging modalities for assessing radiographic tumor response. In patients whom contrast is strictly contraindicated, non-contrast MRI scans and CT chest scans are acceptable. The chest, abdomen, and pelvis must be imaged along with any other known or suspected sites of disease. If more than one imaging modality is used at screening for the same anatomies, the most accurate imaging

modality according to RECIST 1.1 should be used when recording data. The same imaging modality and techniques used at screening should be used for all subsequent assessments. At screening, MRI of the brain with contrast or without contrast if contrast is contraindicated, or CT with contrast when MRI is contraindicated, should be performed in patients with a known history of treated brain metastasis. Additional sites of known disease (including CNS) should be imaged at screening. Refer to the Site Imaging Manual for details of imaging requirements.

After the baseline tumor assessment, radiographic tumor assessments will be obtained in all patients at the time points indicated in [Table 2](#) (with a window of ± 7 days). During safety follow-up, radiographic evaluation will be performed every 4 months until RECIST 1.1-defined progressive disease, withdrawal of consent, death, or initiation of another anticancer treatment.

Tumor assessments should be performed even if dosing is interrupted. Weeks and months are in reference to the calendar week and month and should not be adjusted due to dosing delays/interruptions. Cycle 1 day 1 date is the reference for all visits including tumor assessments visits.

De-identified scans will be collected and, at the Sponsor's discretion, reviewed by independent radiologists using RECIST criteria at a later date, or at any time during the study.

9.2.2.1.1. Tumor Burden Assessments

Tumor measurements will be performed in accordance with RECIST 1.1. Criteria ([Eisenhauer, 2009](#)) ([Appendix 3](#)) and should be done by the same investigator or radiologist for each assessment of a patient, to the extent feasible.

Investigators will assess response to therapy using RECIST 1.1 criteria. RECIST 1.1-defined progressive disease determined by the investigator will be used for clinical management of the patient. RECIST 1.1-based tumor burden assessments will be used for evaluation of efficacy endpoints.

9.2.3. Safety Procedures

9.2.3.1. Electrocardiogram

Local ECGs should be performed before blood is drawn during visits requiring blood draws. A standard 12-lead ECG will be performed at time points according to [Table 2](#). Heart rate will be recorded from the ventricular rate, and the PR, QRS, RR and QT (identify QTcB or QTcF) intervals will be recorded. The ECG strips or reports will be retained with the source.

9.2.3.2. Performance Status

Eastern Cooperative Oncology Group performance status will be performed at the time points according to [Table 2](#). Performance status will be assessed according to ECOG criteria in [Appendix 1](#).

9.2.3.3. Body Weight and Height

Body weight will be assessed using calibrated scales. Patients should void (empty bladder) prior to weight assessment. Patients should be wearing undergarments only and no shoes during weight assessments. Body weight will be recorded to the nearest 0.1 kg.

Height will be assessed at screening only.

9.2.3.4. Vital Signs

Vital signs, including temperature, sitting blood pressure, pulse, and respiration will be collected pre-dose and post-dose at time points according to [Table 2](#). Vital signs will also be taken every hour during the 4-hour observation period following ISA101b administration.

Note: Blood pressure should be measured after the patient has been resting quietly for at least 5 minutes. Blood pressure may be obtained from a seated or recumbent position and should be done consistently throughout the study. When scheduled at the same time as other procedures, vital signs should be measured prior to clinical laboratory assessments, PK, or exploratory sample collection.

9.2.3.5. Physical Examination

A thorough and complete physical examination will be performed at visits specified in [Table 2](#). Care should be taken to examine and assess any abnormalities that may be present, as indicated by the patient's medical history.

Complete physical examination will include examination of head and neck, lungs, heart, abdomen (including liver and spleen), lymph nodes, extremities, and skin, as well as a brief neurologic examination.

Limited physical examination will include examination of lungs, heart, abdomen, skin, and other organ systems at visits specified in [Table 2](#).

9.2.3.6. Laboratory Testing

Hematology, blood chemistry, coagulation, TSH (with reflex T3, free T4), urinalysis, and pregnancy testing samples will be analyzed by the site's local laboratory.

Samples for laboratory testing will be collected at visits according to [Table 2](#). Tests will include:

Blood Chemistry

Sodium	Glucose	Aspartate aminotransferase (AST)
Potassium	Albumin	Alanine aminotransferase (ALT)
Chloride	Total protein, serum	Alkaline phosphatase
Carbon dioxide (bicarbonate)*	Creatinine	Bilirubin (total/direct)***
Calcium	Blood urea nitrogen (BUN)**	Uric acid

*At sites at which the bicarbonate assay is not performed as part of the routine chemistry panel, it may be omitted

**At sites at which a urea assay is performed instead of BUN, the urea assay will be acceptable.

***Total or direct bilirubin may be measured, whichever is standard per site.

Hematology

Hemoglobin	Differential:
White blood cells (WBCs)	Neutrophils
Platelet count	Lymphocytes

Monocytes

Urinalysis

pH	Ketones	Glucose
Specific gravity	Protein	Blood

Other Laboratory Tests

Thyroid Function Tests: Thyroid-stimulating hormone (with reflex T3, free T4) will be tested at visits specified in [Table 2](#) while the patient is on treatment. If TSH is abnormal, T3 and free T4 should be measured at the investigative site's local laboratory. If an investigative site routinely performs total T3 and/or total T4 tests, these measurements will be acceptable in lieu of free T3 or free T4.

Coagulation Tests: Prothrombin time and activated partial thromboplastin time testing will be performed at visits specified in [Table 2](#) while the patient is on treatment. Sites may report INR and activated PTT if it is the standard of care at that site.

Viral Serology Tests: HBV, HCV, and HIV serum antibodies will be tested at visits specified in [Table 2](#).

Pregnancy Tests: Serum β -HCG or urine β -HCG will be measured ≤ 72 hours prior to study drug administration) and serum/urine β -HCG will be measured at all other time points as specified in [Table 2](#).

Abnormal Laboratory Values and Laboratory Adverse Events

All laboratory values must be reviewed by the investigator or authorized designee.

Significantly abnormal test results that occur after start of treatment must be repeated to confirm the nature and degree of the abnormality. When necessary, appropriate ancillary investigations should be initiated. If the abnormality fails to resolve or cannot be explained by events or conditions unrelated to the study medication or its administration, the Medical/Study Director must be consulted.

The clinical significance of an abnormal test value, within the context of the disease under study, must be determined by the investigator.

Criteria for reporting laboratory values as an AE are provided in [Section 10.1.1](#).

9.2.3.7. Additional Samples

Any additional samples (eg, pulmonary effusion fluid, ascites fluid, etc) collected as a part of standard-of-care or symptomatic management while on study may be sent for analysis. These collections are optional but encouraged for further understanding of interactions between patients, disease, and study drugs.

9.2.4. Drug Concentration and Pharmacokinetic Measurements

Samples for cemiplimab concentration will be collected at visits listed in [Table 2](#).

Any unused samples may be used for exploratory biomarker research or to investigate AEs as appropriate.

9.2.5. Immunogenicity Measurements and Samples

Samples for ADA assessment of cemiplimab will be collected at time points listed in [Table 2](#). In response to AESI like anaphylaxis or hypersensitivity, additional ADA samples closer to the event may be collected and analyzed when possible, based on the judgement of the medical investigator and/or medical monitor (in treatment, follow-up, or resumption of treatment). The exact date and time of sample collection must be recorded and entered into the electronic data capture (EDC).

Any unused samples may be used for exploratory biomarker research or to investigate AEs as appropriate.

9.2.6. Pharmacodynamic and Exploratory Biomarker Procedures

In this study, research assessments will be performed to better understand the baseline predictive biomarkers of cemiplimab + ISA101b response that may include but are not limited to tumor tissue analysis of PD-L1 expression and immune cell subsets by IHC or RNAScope, tumor DNA and RNA sequencing. Pharmacodynamic and tumor biomarker samples will be collected at time points according to [Table 2](#), and measurements will be performed to determine treatment effect on the disease and relevant physiological processes. The biomarkers studied are believed to be relevant to the pathophysiology of indication target engagement, mechanism of action of cemiplimab and possible toxicities.

Biomarker assays may include, but will not be limited to, the following:

- Tumor specific and HPV gene panel (circulating tumor DNA sequence profile)
- T cell effector and innate immune cytokine panel (serum cytokines)
- T cell, myeloid cell subset analysis, functional HPV E6/E7 specific T cell assays

9.2.7. Peripheral Blood Biomarkers

Samples for peripheral blood (plasma, serum, and PBMC samples) biomarker assessments will be collected at time points listed in [Table 2](#).

PBMC collection is optional. PBMCs from patients receiving cemiplimab may be used for characterization of immune cell subsets including T cells, B cells, natural killer cells, monocytes, dendritic cells, and subsets of these cell types. Peripheral blood mononuclear cell samples may also be used to assess immune cell function, including T cell activation and proliferation.

9.2.8. Survival Data Collection

Every effort will be made to collect survival data on all patients, including patients who discontinued the study for any reason but have not withdrawn consent to collect survival information. If the death of a patient is not reported, the date of the last patient contact in this study will be used in the determination of the patient's last known date of alive. Use of publicly available information should only be in accordance with local law.

9.2.9. Future Biomedical Research (Optional)

Patients who agree to participate in the future biomedical research sub-study will be required to consent to this optional sub-study before samples are banked in long-term storage. The unused

biomarker samples for study-related research, as well as unused PK and ADA samples, will be stored for up to 15 years after the final date of the database lock. The unused samples may be utilized for future biomedical research. Future biomedical research may include assay development and/or validation, and the samples may be used as references or controls in unrelated experiments. After 15 years, any residual samples will be destroyed. The results of these future biomedical research analyses will not be presented in the CSR.

9.2.10. Pharmacogenomic Analysis (Optional)

Patients who agree to participate in the genomics sub-study will be required to consent to this optional sub-study before collection of a pharmacogenomics-specific whole blood sample. This sample may be collected during screening or any other time point for study-related research (Table 2), and genomic DNA will be extracted for analysis as described below.

The DNA samples for pharmacogenomics analyses will be single-coded as defined by the International Council for Harmonisation (ICH) guideline E15 samples. Samples will be stored for up to 15 years after the final date of the database lock. If there are specific site or country requirements involving the pharmacogenomic analyses with which the sponsor is unable to comply, samples will not be collected at those sites.

The purpose of the pharmacogenomic analyses is to identify genomic associations with clinical (safety or efficacy) or biomarker response to cemiplimab, clinical outcome measures, and possible AEs. In addition, associations between genomic variants and prognosis or progression of cervical cancer or related diseases may also be studied. These data may be used or combined with data collected from other studies to identify and validate genomic markers related to the study drug, target pathway, or cervical cancer and related diseases.

Analyses may include sequence determination or single nucleotide polymorphism studies of candidate genes and surrounding genomic regions. Other methods, including whole-exome sequencing, whole-genome sequencing, DNA copy number variation, methods for quantifying epigenetic modifications, and sequencing of the somatically recombined adaptive immune receptor loci may also be performed, including comparison to DNA extracted from tumor tissue biopsies. The list of methods may be expanded to include novel methodology that may be developed during the course of this study or sample storage period.

10. SAFETY EVALUATION AND REPORTING

10.1. Recording and Reporting Adverse Events

10.1.1. Adverse Events

The investigator (or designee) will seek information on AEs at each patient contact, and record all AEs that occur from the time the informed consent is signed until 90 days after the last study treatment, or until the patient commences another anticancer systemic therapy, whichever comes first. After informed consent has been obtained but prior to initiation of study drug, only the following AEs should be reported:

- SAEs
- Non-SAEs caused by a protocol-mandated intervention (eg, non-SAEs related to invasive procedures such as biopsies)

Other AEs that occur prior to the first treatment should be reported on the medical history CRF.

All AEs after initiation of study treatment and until 90 days after the last study treatment, regardless of relationship to study treatment, will be reported on the AE CRF. Additionally, any SAE or other AE of concern that the investigator believes may be related to study treatment and that occurs later than 90 days after last study treatment, or after the patient has commenced another anticancer systemic therapy (whichever comes first) should be reported.

Study treatment includes cemiplimab and ISA101b.

Information on follow-up for AEs is provided in Section 10.1.2. Laboratory, vital signs, or ECG abnormalities are to be recorded as AEs as outlined in Section 10.1.5.

10.1.2. Serious Adverse Events

All SAEs, regardless of assessment of causal relationship to study treatment must be reported to the sponsor (or designee) within 24 hours. Refer to the study reference manuals for the procedure to be followed.

Information not available at the time of the initial report must be documented in a follow-up report. Substantiating data such as relevant hospital or medical records and diagnostic test reports may also be requested.

In the event the investigator is informed of an SAE that occurs after 90 days after the last dose of study treatment, or after the patient commences another anticancer systemic therapy (whichever comes first), only those SAEs or other AEs of concern deemed by the investigator to be related to study treatment will be reported to the sponsor. The investigator should make every effort to obtain follow-up information on the outcome of a treatment-related SAE until the event is considered chronic and/or stable.

10.1.3. Other Events that Require Accelerated Reporting to Sponsor

The following events also require reporting to the sponsor (or designee) within 24 hours of learning of the event:

Symptomatic Overdose of Study Drug: Accidental or intentional overdose of at least 2 times the intended dose of study drug within the intended therapeutic window, if associated with an AE.

Pregnancy: Although pregnancy is not considered an AE, it is the responsibility of the investigator to report to the sponsor (or designee), within 24 hours of identification, any pregnancy occurring in a female during the study or within 6 months of the last dose of study drug. Any complication of pregnancy affecting a female study patient and/or fetus and/or newborn that meets the SAE criteria must be reported as an SAE. Outcome for all pregnancies should be reported to the sponsor.

Adverse Events of Special Interest (applicable to cemiplimab only): All AESI, serious and nonserious, must be reported within 24 hours of identification using the same reporting process as for SAE reporting, per Section 10.1.2. Adverse events of special interest for this study include the following:

The following will be considered AESI for this study:

- Grade ≥ 2 infusion related reactions
- Grade ≥ 2 allergic/hypersensitivity reactions
- Grade ≥ 3 imAEs (see Section 10.1.3.1)
- An imAE of any grade in a patient previously treated with a PI 3-K inhibitor

NOTE (Applicable to cemiplimab only): An imAE can occur shortly after the first dose or several months after the last dose of treatment. All AEs of unknown etiology associated with drug exposure should be evaluated to determine possible immune etiology. If an imAE is suspected, efforts should be made to rule out neoplastic, infectious, metabolic, toxin or other etiologic causes prior to labeling an AE as an imAE.

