1.3.3. Safety Profile

Clinical experience in approximately 100 patients who have received ISA101 indicates that the most common AEs associated with ISA101 are local ISRs. The ISRs were dose related and observed in approximately 90% of the patients who received the RP2D of 100 µg/peptide. In addition, systemic allergic reactions have been observed, particularly in patients receiving higher doses of 300 µg/peptide (33%) compared to <5% at the 100 µg/peptide dose.

Based on its composition and initial clinical data, ISA101b appears to have a comparable safety profile to ISA101. The available safety data with ISA101b indicate that it has an acceptable safety profile for use at 100 µg/peptide. The most frequent toxicities are local ISRs (predominantly grade 1 to 2). Systemic allergic reactions are potentially the most serious adverse reactions to ISA101/ISA101b.

No overlapping toxicities of ISA101/ISA101b with either chemotherapy (paclitaxel and carboplatin) or anti-PD-1 therapy (nivolumab) have been detected. No autoimmune AEs have been reported in relationship to HPV-16-SLP, ISA101 or ISA101b. Immune-mediated treatment-emergent adverse events (TEAEs) have been reported with anti-PD-1 antibodies. For further information on ISA101b regarding appropriate recommendations and precautions, refer to the ISA101b Investigator's Brochure.

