4.2. Secondary Endpoints

The secondary endpoints are:

- Incidence and severity of TEAEs/adverse events of special interest (AESIs)/serious adverse events (SAEs) and \geq grade 3 laboratory abnormalities during the treatment period and up to 90 days after the last dose of study treatment
- DOR
- PFS
- OS

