10.3. Safety Monitoring

The investigator will monitor the safety of study patient at his/her site(s) as per the requirements of this protocol and consistent with current Good Clinical Practice (GCP). Any questions or concerns should be discussed with the sponsor in a timely fashion. The sponsor will monitor the safety data from across all study sites. The Medical/Study Director will have primary responsibility for the emerging safety profile of the compound, but will be supported by other departments (eg, Pharmacovigilance; Risk Management; Biostatistics and Data Management). Safety monitoring will be performed on an ongoing basis (eg, individual review of SAEs) and on a periodic cumulative aggregate basis.

10.4. Notifying Health Authorities, Institutional Review Board/Ethics Committee, and Investigators

During the study, the sponsor and/or the CRO will inform health authorities, IECs/IRBs, and the participating investigators of any SUSARs (Suspected Unexpected Serious Adverse Reactions) occurring in other study centers or other studies of the active study drug (cemiplimab), as appropriate per local reporting requirements. In addition, the sponsor and/or CRO will comply with any additional local safety reporting requirements. All notifications to investigators will contain only masked information.

Upon receipt of the sponsor's notification of a SUSAR that occurred with the study drug, the investigator will inform the Institutional Review Board (IRB)/Ethics Committee (EC) unless delegated to the sponsor.

Event expectedness for study drug (cemiplimab) is assessed against the Reference Safety Information section of the most recently approved version of the Investigator's Brochure that is effective for expedited safety reporting.

At the completion of the study, the sponsor will report all safety observations made during the conduct of the trial in the Clinical Study Report to health authorities and IECs/IRB as appropriate.

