4.5.2. Adverse Events of Special Interest (applicable to cemiplimab only)

All AEs of special interest (AESI), serious and nonserious, must be reported to the Sponsor within 24 hours of identification. AEs of special interest for this study include:

- Grade ≥ 2 infusion-related reaction (IRR)
- Grade ≥ 2 allergic/hypersensitivity reactions
- Grade ≥ 3 immune-mediated adverse event (imAE)
- An imAE of any grade in a patient previously treated with a PI3-Kinase inhibitor

Note: An imAE can occur shortly after the first dose, several months after the last dose of treatment, or any time in-between. All AEs of unknown etiology associated with drug exposure should be evaluated to determine possible immune etiology. If an imAE is suspected, efforts should be made to rule out neoplastic, infectious, metabolic, toxin or other etiologic causes prior to labeling an AE as an imAE.

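### The product scope of the AESI rule is contradictory for allergic reactions to ISA101b, and the SUSAR text names only cemiplimab

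*Protocol*

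**What the plan says.** **AESI rule.** Protocol 10.1.3 requires AESIs, serious or not, to reach the sponsor within 24 hours. Its heading is "Adverse Events of Special Interest (applicable to cemiplimab only"). The list below that heading is introduced as the AESIs for this study and includes "Grade ≥ 2 allergic/hypersensitivity reactions", with no drug named. The SAP carries the same restriction in a section title: "4.5.2. Adverse Events of Special Interest (applicable to cemiplimab only"). Protocol 10.2.3 defines an AESI in general terms and lists no events. Neither document has a separate AESI list for ISA101b.

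**Endpoint.** Protocol 4.2 makes AESIs part of a secondary endpoint: "Incidence and severity of TEAEs/adverse events of special interest (AESIs)/serious adverse events (SAEs"). The safety objective in Protocol 2.2 concerns the combination.

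**ISA101b.** Protocol 1.3.3 states: "Systemic allergic reactions are potentially the most serious adverse reactions to ISA101/ISA101b." Protocol 8.1 calls ISA101b investigational. Protocol 10.1.1 says "Study treatment includes cemiplimab and ISA101b", and 8.2.2.1 also uses the term study drug for either product.

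**SUSARs.** Protocol 10.4 describes notification of SUSARs for the active study drug, with cemiplimab in brackets, and continues: "Event expectedness for study drug (cemiplimab) is assessed against the Reference Safety Information section" of the Investigator's Brochure. ISA101b is not named in that section.

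**The concern.** The trial tests a combination, and one of its two components is unapproved. The type of reaction that the protocol singles out as potentially the most serious for that component is an allergic one. The AESI list contains the matching item, but under a heading that confines it to the other drug.

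Two things are at stake. First, sites may apply the item differently. One may send a grade 2 hypersensitivity reaction after ISA101b as an AESI within 24 hours, while another records it as an ordinary adverse event. The AESI incidence would then partly reflect how each site read the heading. Second, expectedness decides whether a serious related event is a SUSAR, and the protocol names no reference document for making that decision for ISA101b.

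**Working it through.** The plan states no figure on this point, so there is none to reproduce. The check compares the texts and then sizes the consequence.

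**Step 1. Is the AESI scope clear?**

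| Place | What it implies |
|---|---|
| Protocol 10.1.3, heading | Cemiplimab only |
| SAP 4.5.2, section title | Cemiplimab only |
| Protocol 10.1.3, sentence introducing the list | AESIs for the study, no product limit |
| Protocol 10.1.3, allergic/hypersensitivity item | No drug and no causality condition |
| Protocol 11.4.5.1, adverse event analysis | AESIs identified by preferred term or prespecified grouping |
| SAP 5.8.1 | AESIs tabulated by SOC, PT and grade, with no attribution step |

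The headings point one way and the operative text the other. Protocol 9.2.5, which mentions hypersensitivity as an example of an AESI, concerns cemiplimab antibody sampling and does not settle the matter.

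**Step 2. What happens to a non-serious grade 2 or higher allergic reaction on day 1?** Under Protocol 6.1, ISA101b is given on day 1 and cemiplimab starts on day 8. SAP 4.5 marks this interval as on-treatment time for ISA101b alone.

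- *Headings govern.* The event cannot be a cemiplimab event. It has no 24-hour route and is not in the AESI count. If it led to withdrawal from the study, Protocol 10.1.4 allows 30 days for reporting.
- *List and analysis text govern.* The event is an AESI, reported within 24 hours and counted.
- *Either reading.* It is a TEAE, graded and shown by SOC and PT (SAP 5.8.1). If serious, it goes to the sponsor within 24 hours whatever its cause (Protocol 10.1.2).

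On days 29 and 50, ISA101b follows cemiplimab by about an hour (Protocol 6.1). If the headings govern, AESI status on those days depends on which drug is blamed.

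**Step 3. Is there another table for these events?** SAP 5.8.1 has dedicated tables for infusion-related and injection site reactions, but none for systemic allergic reactions. The hypersensitivity and anaphylaxis SMQs appear only in the optional antibody-association analysis of SAP 5.10.2. Outside the AESI table, allergic reactions would be spread across preferred terms.

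**Step 4. How many patients?** Inputs are N = 105 (Protocol 11.2) and a systemic allergic reaction rate below 5% at 100 µg/peptide (Protocol 1.3.3). The rates below 5% in this table are assumptions.

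Expected number = N × p. Probability of at least one = 1 − (1 − p)^N.

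| Rate p | 105 × p | 1 − (1 − p)^105 |
|---|---|---|
| 0.5% | 0.5 | 41% |
| 1% | 1.1 | 65% |
| 2% | 2.1 | 88% |
| 3% | 3.2 | 96% |
| 5% (ceiling) | 5.3 | 99.5% |

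These are systemic allergic reactions of any grade and seriousness. The affected group is smaller: grade 1 events are not AESIs, and serious events are reported quickly anyway. The documents give no split by grade or seriousness, so the reduction cannot be calculated.

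**Step 5. SUSAR text.** Protocol 10.4 ties both notification and expectedness to cemiplimab. Protocol 8.1 refers to a separate Investigator's Brochure for each product, so a reference source for ISA101b exists but is not named in 10.4.

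**The case against.** The strongest reply is that nothing need be lost. The allergic/hypersensitivity item carries no causality condition and the analysis text works by term, so a reaction after ISA101b could appear in the AESI table in any case. This stands: exclusion is one reading, not an established fact. A reader might infer from the headings that the AESI table certainly omits vaccine reactions, or that attribution is a stated condition. The documents support neither.

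A second reply is that serious cases are covered. Protocol 10.1.2 sends every SAE to the sponsor within 24 hours, and 10.2.2 includes important medical events, with an allergic airway reaction among its examples. There is also a 4-hour observation period with hourly vital signs after ISA101b, and ongoing sponsor review. This stands too, and it confines the AESI gap to non-serious events and to the endpoint count.

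Third, an AESI list is the sponsor's choice. Protocol 10.2.3 ties it to the sponsor's product or program, and the protocol and SAP headings agree. A list confined to cemiplimab would be legitimate if the text were consistent, but it is not, and the safety objective covers both drugs.

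Fourth, 10.4 also commits the sponsor to further local safety-reporting requirements, and the bracketed drug name may be template wording. That may well lead to ISA101b SUSARs being reported, so a reader should not infer that they would go unreported. The sentence still names neither ISA101b nor its reference safety information.

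**Conclusion.** The point holds as a conflict of scope that should be corrected. On the literal reading, non-serious grade 2 or higher allergic reactions to ISA101b lose 24-hour reporting and their place in a secondary endpoint. On the other reading they do not. The text does not say which applies. The missing ISA101b reference for SUSAR expectedness is a separate gap and does not depend on how the AESI list is read.

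The size is small, likely a few patients at most. It would be tempting to say that about 5 of 105 patients would be missing (0.05 × 105 = 5.25). The documents do not support this: the 5% is a ceiling with no stated grade, it comes from a summary of about 100 patients given the predecessor ISA101, and the product includes grade 1 and serious events. The sizing also assumes that ISA101b behaves like ISA101, which Protocol 1.3.3 suggests.

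Two other inferences go too far. Allergic reaction is not described as the main risk of ISA101b: Protocol 1.3.3 names injection site reactions as the most frequent toxicity, and 3.3.3.2 names lack of response as the fundamental risk. Nor would other sites learn late of non-serious reactions because of the AESI wording: AESIs go to the sponsor, and 10.4 notifies investigators of SUSARs, which are serious by definition.

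**What to change.** Reconcile Protocol 10.1.3, Protocol 10.4 and SAP 4.5.2 with Protocol 1.3.3, 8.1, 8.2.2.1 and 10.1.1.

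- **Protocol 10.1.3 and SAP 4.5.2:** state that the grade 2 or higher allergic/hypersensitivity item applies to either study drug, regardless of attribution. This also removes the need to choose between the drugs on days when both are given.
- **Protocol 10.4:** name both cemiplimab and ISA101b for SUSAR notification and expectedness, each assessed against its own Reference Safety Information.
- **If a cemiplimab-only list is intended:** say so consistently, label the endpoint as cemiplimab AESIs, and add a table of systemic allergic and hypersensitivity reactions to SAP 5.8.1.

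The cost is protocol and SAP wording and, for the main option, a few additional expedited reports. No dose or treatment rule changes.
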